### 6.3 STATISTICAL METHODS

Data accrued through this study will be reviewed with statisticians from The Minnesota Medical Research Foundation Chronic Disease Research Group. Repeatedmeasures analysis of variance (ANOVA) will be used to evaluate the effectiveness of the training program for increased neck strength. Relationships among neck-strength parameters and concussion risk and functional outcome measures will be evaluated via logistic and linear regression models. Analyses will be adjusted for sex to evaluate whether the results are independent of gender.

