# 4.5.2 Duration of Investigation

Enrolled subjects may be followed for up to 3 years. The duration of training and assessment for subjects is anticipated to vary by sport and program. However, all subjects will HSR# 17-4360

complete the neck-strengthening training program twice weekly for the duration of time that they are enrolled in the study.

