# **INCLUSION CRITERIA:**

- 1. Involved in programmatic athletic activities with an ongoing duration of at least 4 weeks.
- 2. Written informed consent obtained by the subject or subject's legal guardian.
- 3. Written assent from subjects ages 8 years old and above
- 4. Subject is between the ages of 5 and 22 years, male or female.

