#### 4.6 STUDY TREATMENT

Subjects will engage in an instructor-led, supervised, manual-resistance training program twice weekly. At each session, subjects will perform a variety of nonweighted resistance exercises, previously shown in a clinical trial to be safe and effective for use in pediatric populations (ClinicalTrials.gov identifier, NCT02455037) and lightly weighted exercises using barbells, and commercial neck strengthening equipment (eg, NekkDekk and/or IronNeck).

The effectiveness of the strength training regime over time will be assessed by measuring neck girth and neck strength at the beginning and end of training sessions at 6-month intervals, for as long as the subject continues the sport program or until he/she leaves the study.

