### 6.2 OUTCOME ASSESSMENT

Outcomes will be assessed by an experienced researcher with neurologic and cognitive evaluations that are commercially available and validated in traumatic brain injury or cognitive dysfunction. Subjects will be followed for a minimum of 4 weeks after enrollment and a minimum of 1 week following a concussive event unless they or their legal guardians choose to leave the study.

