### 6.4 SAMPLE SIZE DETERMINATION

Sample size estimates were calculated based on unpublished data indicating an incidence of concussion of 11%, and published data on the reduction in concussion risk associated with increased neck strength. Based on this information, a sample of size of 1198 subjects would be needed to detect a correlation of R=0.25 between neck strength and a reduction in the severity of concussion symptoms (based on cognitive assessment scores) with a power of 0.8 at alpha=0.05. Assuming attrition of 15-20%, we therefore believe that approximately 1500 subjects will be needed.

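### Repeated-measures ANOVA is named for the strength gain from training, but the design yields series of unequal length; a linear mixed model fits it better

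*Protocol*

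**What the plan says.** Section 6.3 states that repeated-measures "analysis of variance (ANOVA) will be used to evaluate the effectiveness of the training program for increased neck strength". The data-analysis entry of Table 1 names the same method. Neither place gives the variant, the occasions to be analysed, or a rule for missing measurements.

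Several other parts of the protocol determine what the strength data will look like:

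- Section 4.5.2: "Enrolled subjects may be followed for up to 3 years", and "The duration of training and assessment for subjects is anticipated to vary by sport and program".
- Section 4.6: neck girth and strength are taken both before and after a session, and this is repeated "at 6-month intervals, for as long as the subject continues the sport program or until he/she leaves the study".
- Section 4.5.5, first inclusion criterion: "Involved in programmatic athletic activities with an ongoing duration of at least 4 weeks". Section 6.2: "Subjects will be followed for a minimum of 4 weeks after enrollment".
- Section 6.4: "Assuming attrition of 15-20" percent.
- Table 1: the study lasts about 3 years in all, and the schedule lists the 6-monthly strength assessments under weeks 4 to 52.
- Sections 4.8.3 and 4.8.4: strength is measured again within 1 day of a diagnosed concussion and, if symptoms persist, at 7 days.

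**The concern.** Classical repeated-measures ANOVA treats time as a fixed set of occasions shared by all subjects. A subject without a value at one of them does not fit the layout, and the usual default is to leave that subject out. Here unequal length is part of the design: one athlete may be in a program of a few weeks and another may be followed for 3 years.

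Two things are at stake. Strength values collected from subjects with partial series would go unused. The estimated gain would also rest on those who stayed longest, who may not respond like the rest. In a single-arm study the within-subject change in strength is the direct evidence that the training raises strength, so its estimate should use the data that are collected.

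**Working it through.** **1. The one stated figure that bears on incomplete follow-up.** Section 6.4 goes from 1198 to about 1500 subjects. With N/(1 − d): 1198/0.80 = 1497.5, so 1498; 1198/0.85 = 1409.4, so 1410. The 1500 is reproduced at 20% attrition. It belongs to the correlation with symptom severity. No sample size or power is stated for the ANOVA, so there is none to recompute.

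**2. Does the mechanism hold?** A classical repeated-measures ANOVA routine was run on simulated series for 300 subjects with 1 to 7 occasions each. It stopped because the data were unbalanced. A linear mixed model ran on the same data and used all 300. Only 15% of these subjects had all seven values, but that share follows from the lengths chosen for the simulation (about 1 in 7) and says nothing about this trial.

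**3. How large could the effect be? An illustration.** The occasions are taken as 0, 6 and 12 months, in line with weeks 4 to 52 in Table 1. The only input from the protocol is 20% attrition. The assumptions are:

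- leaving is spread evenly over months 1 to 36;
- a fraction m of visits is missed independently at each of months 6 and 12;
- dropped subjects gain half as much as those kept.

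Still followed at month 6: 1 − 0.20 × 5/35 = 0.971. Still followed at month 12: 1 − 0.20 × 11/35 = 0.937.

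The share with all three values is 0.937 × (1 − m)². Divided by 0.971, this gives p, the share kept among subjects with some follow-up. The overstatement of the mean gain is 1/(p + (1 − p) × 0.5) − 1.

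| Missed per visit (assumed) | All three values | p | Overstatement |
|---|---|---|---|
| 0% | 0.937 | 0.965 | 1.8% |
| 5% | 0.937 × 0.9025 = 0.846 | 0.871 | 6.9% |
| 10% | 0.937 × 0.81 = 0.759 | 0.781 | about 12% |

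The divisor 0.971 ignores missed visits. Allowing for them at 10%, the share with baseline and at least one later value is 0.937 × 0.99 + 0.034 × 0.90 = 0.959. Then p = 0.759/0.959 = 0.792 and the overstatement is 1/(0.792 + 0.208 × 0.5) − 1 = 11.6%, so the result stays near 12%.

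**4. What drives the range.** Attrition alone gives about 2%. The rest comes from the missed-visit rate, which the protocol does not state. If dropped subjects gained as much as the others, the overstatement would be zero at any p. The illustration also leaves out the variation in program length. The protocol describes that variation but gives no distribution for it, so its effect cannot be computed.

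**The case against.** The strongest objection is that the protocol nowhere says partial series are excluded. It gives a method label, and that label is sometimes used for models that keep partial series. The variant, the occasions and the missing-data rule are commonly left to an analysis plan, which is not at hand, and section 6.3 says the data will be reviewed with statisticians. This stands as far as it goes: a reader might infer that such subjects are discarded, but that is the usual default of the classical method and not a rule in the document. It does not remove the point, because the protocol does name a method and its plain reading is the one that suits the stated design poorly.

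A reader might also infer that hardly anyone would be analysed, since 3 years of 6-monthly visits make seven occasions and only subjects enrolled at the very start of a 3-year study could complete them. The document does not support this. It does not say that all seven occasions enter one ANOVA, and Table 1 lists the assessments under weeks 4 to 52.

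Nor does the document support a definite bias of 12%. That value needs the assumed 10% missed visits and the assumed half gain. Most subjects dropped in that case would have missed a visit at random, and there is no stated reason why they should gain less.

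Finally, the primary objective and hypothesis (sections 4.3 and 4.4) concern neck strength and concussion, which section 6.3 analyses by logistic and linear regression. This stands and limits the weight of the point.

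**Conclusion.** The concern holds in a limited form. The protocol names a method that, in its classical form, needs complete series on common occasions, while its own design produces series of unequal length. The likely consequences are unused data and an estimate tilted toward athletes who stay longest.

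The size cannot be derived from the document. The range of about 2% to 12% at 12 months is an illustration under the assumptions in the working. Subjects who leave before their first 6-month measurement are a separate matter: with a baseline value only, they add little about change under any method.

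This is a secondary analysis. The change is worth making because it is nearly free.

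**What to change.** In section 6.3 and the data-analysis entry of Table 1, replace repeated-measures ANOVA by a likelihood-based linear mixed model for neck strength, specified as follows:

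- all available scheduled strength values enter, so partial series are kept;
- time is the actual time since baseline;
- each subject has a random intercept, and a random slope if the data support it;
- sex is included as already planned;
- because strength is taken before and after the session at each 6-month occasion (sections 4.6 and 4.8.2), the model has a before/after term, or only the pre-session values are used;
- measurements made after a concussion (sections 4.8.3 and 4.8.4) are kept out of this model or flagged in it.

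If a model of this kind is what the present label means, a sentence saying so is enough.

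The cost is a change of wording. No new data are needed, and no stated sample size or power changes. The model is valid if missing values are missing at random given the observed data. It does not cure departure that depends on unobserved strength, but it asks less of the data than a complete-series analysis.

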# 4 STUDY PROTOCOL

### 4.1 **OVERVIEW**

This project has the following goals:

- 1. Determine whether baseline measurements of neck strength correlate with the incidence, severity, and duration of concussion symptoms;
- 2. Determine whether a standardized neck strengthening training regime reduces the risk of concussion and the severity and duration of symptoms; and
- 3. Determine whether the relationships between neck strength and the clinical symptoms of concussion are independent of gender.

Subjects aged 5 to 22 who are involved in organized, academic or community-based contact/collision sports activities at Gustavus Adolphus College, member schools of the Independent Metro Athletic Conference (IMAC) conference, and The Sanneh Foundation participate in an instructor-led neck-strength training program. Subjects enrolled in the study will be followed for up to 3 years to assess whether the incidence, severity, and duration of concussion symptoms varies as a function of neck strength in young athletes. Anthropometric measurements, neck strength parameters, cognitive assessments, and an eye-tracking assessment will be performed for each subject at baseline, and at yearly intervals thereafter in the absence of a reported head injury. In addition, anthropometric and neck-strength measurements will be recorded at regular intervals during the study to quantify the effectiveness of the strength training regime. Subjects diagnosed with concussion during the study will be assessed for the severity and duration of postconcussion symptoms using eyetracking methodology and traditional cognitive assessments. Clinical outcomes will be assessed immediately following a concussive event and monitored by research staff until symptoms resolve. Data will be collected by onsite study volunteers trained by [name] or another member of the Brain Injury Research Lab staff at HCMC. All aspects of the study design will be overseen and approved by [name].

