# Data analysis

Repeated-measures analysis of variance (ANOVA) will be used to evaluate the effectiveness of the training program for increasing neck strength. Relationships among neck-strength parameters and concussion risk and functional outcome measures will be evaluated via logistic and linear regression models. Analyses will be adjusted for sex to evaluate whether the results are independent of gender.

SCHEDULE

Week 1: Initial visit or call prior to enrollment to obtain informed consent; Baseline assessments made within 72 hours of enrollment Weeks 4 to 52: Assessments of neck strength made at 6-month intervals (+/- 3 days)a

Weeks 4 to 52: Assessments of concussion symptoms (if applicable) until symptoms resolve.

HSR# 17-4360

	
 
Time-of-event (within 1 day of event): Cognitive and eye-tracking assessments
 
Days 1-7 after event: Daily subset of cognitive assessments
 
Day 7: Eye-tracking assessment, neck-strength measurement
 
Weeks 4, 8, and 12 after event (+/- 3 days): Cognitive assessments
 

	a The neck-strengthening training regime will be administered for the length of the subject's sport program and during the period(s) of time corresponding to the subject's regular athletic training schedule.
BLINDING	This study is nonblinded.

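### Concussion incidence is assigned to sex-adjusted logistic regression although follow-up may run from 4 weeks to 3 years, so unequal time at risk is ignored on the natural reading

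*Protocol*

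**What the plan says.** Section 6.3 of the protocol, repeated in the data-analysis entry of Table 1, states: "Relationships among neck-strength parameters and concussion risk and functional outcome measures will be evaluated via logistic and linear regression models". One covariate is named: "Analyses will be adjusted for sex to evaluate whether the results are independent of gender". Goal 1 in section 4.1 ties the incidence question to strength at baseline: "Determine whether baseline measurements of neck strength correlate with the incidence, severity, and duration of concussion symptoms". Incidence is also part of the primary objective (4.3) and the primary hypothesis (4.4).

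On length of observation:
- Section 6.2 sets the floor: "Subjects will be followed for a minimum of 4 weeks after enrollment".
- Section 4.5.2 sets the ceiling: "Enrolled subjects may be followed for up to 3 years". It adds: "The duration of training and assessment for subjects is anticipated to vary by sport and program".
- The first inclusion criterion admits short programs: "Involved in programmatic athletic activities with an ongoing duration of at least 4 weeks".
- Footnote a of Table 1 ties training to the subject's "regular athletic training schedule", so enrolled time need not all be time in sport.

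The protocol mentions no person-time, offset, censoring rule or fixed risk window.

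**The concern.** Whether a subject is ever concussed depends on how long he or she is watched. A plain logistic model of concussed versus not concussed leaves that out, and adjusting for sex does not restore it.

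If stronger athletes are followed longer, they have more time to be concussed. The model can then hide a real protective effect or make strength look harmful. If stronger athletes leave sooner, the bias reverses and can mimic protection. A link is plausible because subjects aged 5 to 22 come from a college, conference schools and a community foundation, and both strength and length of follow-up may differ between these groups. At stake is the incidence part of the primary question.

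**Working it through.** The plan has no figure of its own for the incidence analysis. The 1198 in section 6.4 concerns a correlation with symptom severity, and this point does not depend on it.

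**Inputs from the protocol.** Floor 4 weeks (6.2); ceiling 3 years = 156 weeks (4.5.2); concussion incidence 11%, with no time unit (6.4). Ceiling over floor is 156/4 = 39. This is the permitted range, not an expected spread.

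**Risk from time alone.** Assuming a constant hazard, risk by week t is 1 - 0.89^(t/52) if 11% is a one-year risk, and 1 - 0.89^(t/156) if it is a three-year risk.

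| Reading of 11% | 4 weeks | 52 weeks | 156 weeks |
|---|---|---|---|
| per year | 0.9% | 11% | 29.5% |
| over 3 years | 0.3% | 3.8% | 11% |

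On either reading, time at risk alone changes the risk more than 30-fold between floor and ceiling.

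**Effect on the test of neck strength.** Simulation with N = 1200, 2000 replicates per case, two-sided 5% tests, sex-adjusted models, constant hazard and no true effect. Baseline strength and follow-up are linked by a Gaussian copula. The follow-up patterns and correlations are assumptions. "Wide" covers three patterns: log-uniform 4-156 weeks, uniform 4-156 weeks, and thirds at 12, 52 and 156 weeks. Entries are logistic false-positive rates.

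| Reading, follow-up | corr. 0 | 0.1 | 0.2 | 0.3 |
|---|---|---|---|---|
| per year, wide | 5-6% | 12-18% | 32-49% | 65-84% |
| per year, 80% full 3 years | 5% | 7% | 10% | 19% |
| over 3 years, wide | 4-6% | 7-9% | 13-21% | 25-42% |
| over 3 years, 80% full 3 years | 5% | 6% | 7% | 9% |

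Cox regression stayed at 4.2-6.4% in every constant-hazard null case. To give the scale: in the thirds pattern, correlation r means that the 156-week group is 2.18 × r SD stronger than the 12-week group, so r = 0.2 is 2.18 × 0.2 = 0.44 SD.

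**Direction and independent check.** A separate simulation (N = 1198, 500 runs, uniform follow-up, 11% per year, no true effect) gave logistic coefficients of +0.122 and -0.123 per SD at correlations +0.2 and -0.2. It rejected in 33% and 34% of runs. A complementary log-log model with a log-time offset gave about 0, with rejection in 5% and 7%.

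**Power.** For a true hazard ratio of 0.75 per SD, correlation 0.2 and 11% per year, logistic versus Cox power is 16 vs 79% (log-uniform), 64 vs 98% (uniform 4-156), 34 vs 96% (thirds) and 99 vs 100% (80% full). On the three-year reading the same patterns give 10 vs 41%, 30 vs 67%, 19 vs 61% and 78 vs 89%.

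**Does changing the model suffice?** Section 2 reports higher concussion risk in younger athletes, so age may drive strength, follow-up and hazard together. Assumptions: age-strength correlation 0.6, strength-follow-up correlation 0.2, hazard ratio 0.8 per SD of age, no strength effect, N = 1200, 400 runs, 11% per year.

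| Follow-up | Cox, sex only | Logistic, sex only |
|---|---|---|
| uniform 4-156 weeks | 39% | 6% |
| thirds | 37% | 8% |
| 80% full 3 years | 62% | 38% |

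Here the two biases partly cancel in the logistic model: age makes strength look protective, and longer follow-up makes it look harmful. Adding age returned Cox to 3-8%. A second set of runs at hazard ratio 0.8 gave 39-68% for a sex-only time-to-event model, 4-38% for logistic, and about 4-11% once age was added. At hazard ratio 0.9 neither sex-only model was consistently better (Cox 6-21%, logistic 5-19%).

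**Seasonal risk.** With an assumed 13-week season each year starting at enrolment and correlation 0.2 or 0.3, a Poisson model with a calendar-time offset rejects in 6-39% of null trials; with in-sport time it rejects in 4-6%. If season length (13 or 39 weeks a year) also varies with strength, Cox on calendar time gives 8-29% and Cox on in-sport time 4-6%.

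**The case against.** The strongest objection is that one sentence naming model families leaves the outcome window, time at risk and further covariates to an analysis plan that is not shown. The wording does not exclude a person-period logistic model or a fixed risk window, and either would remove or reduce the problem. This stands in part. The protocol nevertheless chose the model family and a covariate for a design that it expects to have unequal follow-up, so clarification is needed even on the kindest reading.

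A second objection stands in full: the harm needs a link between strength and follow-up that no section quantifies. With no link, the logistic test keeps its level. With most subjects followed for 3 years, the harm is modest. If follow-up beyond the season carries no risk, it can vanish: in the seasonal cases where follow-up ended within a year, logistic stayed at 4-6%.

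Several stronger readings are tempting but not supported:
- A reader might infer from the weeks 4 to 52 entry in Table 1 an alternative 52/4 = 13-fold range of follow-up. That entry is an assessment schedule and does not say how long subjects are followed.
- A reader might take the highest rates (65-84%) as the expected error. They need correlation 0.3, wide follow-up and the per-year reading together.
- A reader might take sex to be the only permitted covariate. The text names sex but does not say that nothing else may enter.
- A reader might conclude that a sex-adjusted Cox model is a sufficient repair. The age calculation shows that it can be worse than the current plan.
- A reader might extend the point to the sample size. That rests on severity scores, which this point leaves untouched.

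**Conclusion.** The point holds in a conditional form and should be fixed, with moderate confidence. On the natural yes/no reading, the stated analysis of incidence ignores time at risk in a design that allows 4 weeks to 3 years. The neck-strength estimate is biased if baseline strength is related to length of follow-up. At an assumed correlation of 0.2, no true effect and 11% per year, false positives are about 10% when 80% are followed for the full 3 years and about 30-50% when follow-up varies widely. At correlation 0 they stay near 5%. The documents do not say which case applies, whether a link exists, or what period the 11% covers. Incidence is one of three outcomes in the primary hypothesis, and the linear regression of severity is not affected.

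**What to change.** In section 6.3 and Table 1, replace logistic regression for concussion incidence with a model that accounts for time at risk. One suitable choice is Cox regression for time from enrolment to first concussion, censored at exit or study end.

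- **Exposure:** baseline neck strength, as in goal 1.
- **Covariates:** age and sport/program as well as sex, because these can drive strength, follow-up and hazard together.
- **Time at risk:** record an exit date for each subject. Where season dates are available, count in-sport time. A Poisson or negative binomial model is acceptable only with in-sport time as the offset.
- **Severity:** keep linear regression.
- **Goal 2:** do not present a time-updated strength covariate as the effect of the training program. All subjects train, and strength is re-measured only every 6 months, so subjects followed for less than that normally have only a baseline value.

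Enrolment is already defined in section 4.5.4, and the assessment within 1 day in section 4.8.3 gives the means to date the concussion. The cost is one exit date per subject, season dates if in-sport time is used, and slightly more analysis work. Season dates across many sports and programs are the larger burden. Both kinds of date are best collected prospectively, so the change should be made early. No extra subjects or visits are needed.

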# 4.5 STUDY ELIGIBILITY AND ENROLLMENT

#### 4.5.1 Study Population

Subjects will be youths aged 5 to 22 who are involved in one or more academic or community-based organized contact/collision athletic sports program(s). Approximately 1500 students will be recruited from Gustavus Adolphus College, member schools of the Independent Metro Athletic Conference (IMAC) conference, and The Sanneh Foundation, and enrolled in the study. The study population will be composed of players from multiple sports, and at a broad range of competitive levels. Study-site coordinators and/or trainers will be advised of the purpose and procedures of the study and will refer subjects to the Investigator for consideration. Subjects who meet all inclusion/exclusion criteria and have appropriate consent to participate in the study may be enrolled. The study is open to all races and both genders.

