# 4.9 CONCUSSION AND ADVERSE EVENT REPORTING

Athletic trainers will inform study site coordinators if a concussive event is suspected. The subject will be removed from activity and ultimately returned to activity as per their school or program protocol. The study site coordinator will immediately inform the Investigator of the event.

Monitoring of potential adverse events will be performed on a continuous and ongoing manner by the Investigator, research staff, and/or experienced athletic trainers at each study site. The nature of each adverse event, date and time of onset (when appropriate), outcome, frequency, maximum intensity, action taken, and attribution of each event will be recorded to identify those that are potentially related to the intervention (ie, the training regime). If an adverse experience increases in frequency or severity during the study period, a new record of the experience will be started.

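### Section 6.3 makes no allowance for clustering by school or program, so if run as written the standard errors for strength versus incidence and for strength change are likely too small

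*Protocol*

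**What the plan says.** Section 6.3 of the protocol names the models: neck strength in relation to "concussion risk and functional outcome measures will be evaluated via logistic and linear regression models", with repeated-measures ANOVA for whether training raises neck strength. Sex is the only adjustment given. Neither 6.3 nor 6.4 mentions site, school, program, a random effect, a robust variance or a design effect. Section 6.4.1, on complications for the analysis, discusses only an unequal split of the sexes.

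Other sections describe a grouped study:

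- **Setting.** Table 1 calls the study multicenter and places recruitment and enrollment at schools and community facilities. Section 4.5.1 lists a college, the schools of one conference and a foundation, and adds: "The study population will be composed of players from multiple sports, and at a broad range of competitive levels". Ages run from 5 to 22.
- **Training.** Section 4.6: "Subjects will engage in an instructor-led, supervised, manual-resistance training program twice weekly". Section 4.5.2 expects the length of training to differ by sport and program.
- **Case finding and aftermath.** In section 4.9 local athletic trainers report suspected events, and the athlete is "ultimately returned to activity as per their school or program protocol".

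**The concern.** Athletes at one school or program share instructors, the trainers who notice and report suspected concussions, a level of exposure, and local rules for return to activity. Their outcomes are therefore likely to be positively correlated. Neck strength probably clusters too, since a college and a youth community program differ in age and sport. When outcome and exposure both cluster, ordinary logistic or linear regression gives a standard error for the slope that is too small. Repeated-measures ANOVA allows for correlation within a subject, not between subjects who train together.

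At stake are the confidence intervals and p-values for two results: the association of neck strength with concussion incidence, which belongs to the primary objective (4.3) and hypothesis (4.4), and the rise in strength that is meant to show that training works. Both could look more precise than they are.

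**Working it through.** **1. The plan's own sample size.** Section 6.4 starts from "unpublished data indicating an incidence of concussion of 11" per cent, aims to "detect a correlation of R=0.25 between neck strength and a reduction in the severity of concussion symptoms" "with a power of 0.8 at alpha=0.05", and concludes that "a sample of size of 1198 subjects would be needed". The nearest route is Fisher's z for one correlation among independent concussed subjects, two-sided:

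n = ((1.960 + 0.842) / atanh(0.25))² + 3 = (2.802 / 0.2554)² + 3 ≈ 123.3, so 124 concussed.

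124 / 0.11 = 1127.3, so 1128 subjects. This does not reproduce 1198, which is about 6% higher (1198 / 1128 = 1.06). The attrition step does reproduce: 1198 / 0.80 = 1498, or about 1500. I see no term for clustering in this route. The failure to reach 1198 exactly is a separate matter and carries no weight here.

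**2. Inputs for the design effects.** All are assumptions, because the protocol gives no ICC and no cluster size:

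- cluster size m: 25–50 athletes (about 24–48 clusters among 1198);
- outcome ICC: 0.01–0.05;
- neck-strength ICC: 0.3–0.5;
- ICC of strength change: 0.01–0.05.

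**3. Formulas.** Clusters are taken as equal in size.

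- Slope on an exposure measured in individuals: DE = 1 + (m − 1) × ICC(outcome) × ICC(strength).
- Mean change: DE = 1 + (m − 1) × ICC(change).
- Real two-sided type I error of a nominal 5% test that ignores clustering: 2 × [1 − Φ(1.96 / √DE)].

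**4. Results.**

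| Analysis | Case | DE | Type I error |
|---|---|---|---|
| Strength–incidence slope | Low: 1 + 24 × 0.01 × 0.3 | 1.07 | about 6% |
| Strength–incidence slope | High: 1 + 49 × 0.05 × 0.5 | 2.23 | about 19% |
| Strength–incidence slope | Strength ICC = 0 | 1.00 | 5% |
| Mean strength change | Low: 1 + 24 × 0.01 | 1.24 | about 8% |
| Mean strength change | High: 1 + 49 × 0.05 | 3.45 | about 29% |

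**5. A second setting for the slope.** Twenty clusters of about 60 (1198 / 20), strength ICC 0.3 and outcome ICC 0.01–0.05 give DE 1.18–1.88, true standard errors 8%–37% larger than the naive ones, and type I error of about 7%–15%. The conclusion does not hang on one choice of cluster size.

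**6. Severity among the concussed.** At 11% incidence a cluster of 25–50 holds about 2.75–5.5 cases. With the same ICC ranges, the slope's DE runs from 1 + 1.75 × 0.01 × 0.3 = 1.01 to 1 + 4.5 × 0.05 × 0.5 = 1.11, so type I error stays at about 5%–6%.

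**The case against.** The strongest objection is that this belongs in a statistical analysis plan, which is not at hand. Section 6.3 names families of models. It does not say that athletes are treated as independent or that site is excluded, and a logistic model with a cluster-robust variance would still fit its wording. That stands in part: independence is inferred from the methods named and is not declared. But the protocol itself fixes the models and names an adjustment, and a reader who ran them as written would ignore clustering.

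Four stronger readings are tempting, and the documents do not support them.

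- *Standard errors are certainly too small.* Neck strength is measured on individuals, so the bias in the slope depends on the product of two unknown ICCs and vanishes if either is zero. At the low end of the assumed range it is slight.
- *Athletes are recruited, trained and diagnosed by team.* Team is not described as a unit. The documented units are schools, programs and facilities. Trainers report suspected events only, while section 6.2 has an experienced researcher assess outcomes. The school's own protocol governs removal from and return to activity, not scoring.
- *The powered severity analysis is undermined.* A large loss can be produced: 10 clusters, ICC 0.10 and neck strength wholly shared within cluster give DE 2.22 and power 0.48, against 0.826 for about 132 independent cases. That is a deliberate extreme. Under the ranges above the effect is small.
- *Correcting the standard errors makes the training effect interpretable.* In a single-arm study of growing subjects followed for up to 3 years, strength may rise without training. The 8%–29% describes only how badly the test of no mean change is calibrated.

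**Conclusion.** The point holds in conditional form. Section 6.3 names methods that, run as written, ignore correlation between athletes in the same school or program, although the protocol describes grouping in recruitment, training and the flagging of suspected events. Standard errors for the strength–incidence association and the mean strength change are likely too small. The likely size ranges from slight to material for the slope, and is larger for mean change because no exposure ICC dampens it. All of this rests on assumed ICCs and cluster sizes, equal clusters and a large-sample normal test. That neck strength differs between sites is an inference from the age range and mix of sports, not a stated fact.

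**What to change.** In section 6.3, state that the logistic, linear and strength-change models account for clustering by school or program, and by sport within site where recorded. Either generalized estimating equations or cluster-robust standard errors with a small-sample correction, or a random intercept, would serve. The correction matters because the number of sites may be modest. State also that each subject's site and program are kept in the dataset.

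The cost is a few sentences and two variables that should be on hand, since enrollment runs through site coordinators (4.5.4). Sport history is already collected at screening (Table 1). Intervals will be somewhat wider. The change corrects the variance only: differences between sites in age, sport and competitive level can still confound the strength–concussion association and need to be handled separately.
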